# Mobile Behavioral Ecological Momentary Assessment and Intervention in Rakai, Uganda: A Pilot Study

## 1. Abstract

Ecological Momentary Assessment and Intervention (EMAI) is an emerging technique for gathering richer and more relevant data through repeated, longitudinal sampling of participants in their natural setting in order to deliver real-time interventions. Challenges with instilling healthy behaviors are well documented. These challenges are magnified in low and middle income countries (LMICs) where significant social and structural barriers to care often exist. The rapid emergence of mHealth (mobile technologies for health), including growing access to low-cost smartphones, now allows for unprecedented advancements in and novel research on mHealth applications in LMICs. We therefore propose a pilot EMAI study of health behavior in Rakai, Uganda.

This study aims to demonstrate that it is feasible and acceptable to use smartphones in a LMIC to collect near real-time, geolocated behavioral information and to send tailored health messages based upon this data. This proposal will provide unique insights into the geospatial/temporal epidemiology of health behaviors, generate preliminary estimates of intervention impact, and establish an evidence-base for future large-scale, randomized EMAI mHealth trials. This study will be nested within the Rakai Health Sciences Program's (RHSP) ongoing Rakai Community Cohort Study (RCCS).

Our main study objective is to conduct a pilot EMAI study among current RCCS study participants. Participants will be given a smartphone with an application that will collect GPS-based geolocations and ask assessment questions (e.g. diet/alcohol, smoking, and sexual behaviors). Using participants' responses, the application can deliver tailored intervention health messaging to participants using pre-programmed algorithms. During Days 1-30 of follow-up, all participants will receive assessment questions only to establish baseline behaviors. During Days 31-90, participants will be randomized to either continuing with assessment questions only (control arm) or to also begin receiving intervention messaging (intervention arm). The randomized design will allow for calculation of an estimate of EMAI effect on diet/alcohol, smoking, and sexual behaviors which will be used to design future, large-scale randomized controlled trials of EMAI.

Secondary objectives of this study proposal are to assess processes, facilitators, and barriers to EMAI using a mixed methods (quantitative and qualitative) approach. Also, to assess EMAI validity and relevance, we will describe and compare EMAI-collected behavioral data with traditional questionnaire-collected data.

Study hypotheses are as follows: **EMAI can be successfully implemented in Uganda, and participants receiving intervention messaging will have improved self-reported health behaviors compared to controls; EMAI will be feasible and acceptable by this population; and, EMAI-collected data will correlate with traditional questionnaire-collected data.**

This is the first study to our knowledge of EMAI in sub-Saharan Africa. If this novel data collection and intervention method is proven to be robust, feasible and acceptable, it could serve as an innovative platform for the future delivery of real-time, tailored, geolocated mHealth interventions, a potentially profound method for improving health.

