## 3. Background

**Smartphone-based mHealth is a potentially transformative technology in low and middle-income countries (LMIC).** The growth of mobile phones in LMIC has been remarkable. Initial mobile growth primarily began with “dumb” or feature phones, i.e. mobile devices with limited features and internet connectivity. These devices were rapidly leveraged for health care purposes as part of a “first wave” of applications based primarily on SMS (short message service) technology. Mobile infrastructure has progressively expanded in LMICs and more recently, smartphones have been steadily increasing in number with an estimated 19.8% penetration in 2013, up from 1.6% in 2008. With the increasing adoption of smartphones in LMICs, a “second wave” of mHealth innovation based upon networked, data-driven applications is possible.

**EMAI may outperform traditional methods of data collection and behavioral intervention.** Ecological Momentary Assessment and Intervention (EMAI) is an emerging technique for gathering richer and more relevant data through repeated, longitudinal sampling of participants and intervening in real-time in their *natural setting*. Compared to traditional assessment of human behavior, e.g. questionnaires and interviews, Ecological Momentary Assessment (EMA) appears to reduce recall bias, improve validity by collecting data in the real world, and enable capture of dynamic processes over time, which has also been supported by our own studies which have collected reliable data on geo-located, sensitive behaviors such as drug use, mood, alcohol intake, and sexual behaviors. Ecological Momentary Intervention (EMI) has benefits beyond traditional interventions by allowing for more temporally and spatially appropriate interventions, extending care beyond traditional health facilities and into the individual’s natural setting. Smartphones have revolutionized access to EMAI and provide a growing platform for health-related assessment and intervention in LMICs.

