**Recruitment.** As part of a detailed written informed procedure, RCCS participants have consented to be contacted for future studies. We will enumerate a list of current RCCS participants with key demographics, and, as described above, we will purposely select participants meeting our study population composition goals. We will begin with recruitment via RCCS in locations where it is actively conducting its continual surveys of the Rakai community, asking participants as they undergo the RCCS survey if they would also like to participate in this nested study. If we are unable to conveniently obtain our desired sample via ongoing survey activities of RCCS, we will send trained staff to recruit RCCS participants from communities in which RCCS has recently conducted surveys. Eligible participants will be asked to complete a written informed consent procedure (see Section 8 below) in order to enter this specific study.

**Participant-related Procedures.** *Participant training.* After recruitment, participants will undergo a ~30-60 minute training session. A brief training curriculum will be used consisting of basic phone use,

Date: March 30, 2015

Principal Investigator: [name], MPH

Application Number: IRB00065934

contacting the study team, and detailed instruction on EMAI application use. Participants will be required to demonstrate proficiency with the EMAI interface prior to receiving a study smartphone. The first 48 hours after the participant has the phone will be a “run-in” period to allow for troubleshooting of device problems and to allow participants to become familiar with the EMAI application procedures.

*Follow-up (Days 1-30, Baseline Behaviors).* After the run-in period, all participants will receive assessment questions only for a 30 day period in order to establish baseline behaviors. After completing this initial 30 day period, participants will be required to return to the study office to complete a short questionnaire (see Aim 3) and to be randomized to the second phase of follow-up.

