*Follow-up (Days 31-90, Randomized Evaluation).* After completing the Day 30 questionnaire, participants will be randomized using a computerized random number generator, in a 1:1 ratio, to either continue receiving assessment questions only (control arm) or to also begin receiving intervention messages (intervention arm). After reaching 60 and 90 days of follow-up, participants will return to the study office to complete a brief questionnaire on behaviors and experiences with the phone. After 90 days of follow-up participants will also return their phones to study staff.

*Logistics.* Phones will be preloaded with airtime. If additional airtime is needed, participants can “beep” (call and hang up, no cost to caller) study staff to transfer airtime to phones using locally available services.

*Smartphone loss/theft.* Installed software will allow for GPS-locating of lost/stolen phones and can remotely wipe data on phones as needed. Participants will be notified that they will not be eligible for their incentives if they lose or have their phones stolen. These participants will remain in all study analyses (intention-to-treat) but will not receive a second phone.

*Smartphone malfunction.* Participants will be asked to communicate with study staff either in-person or remotely should their smartphone malfunction. Malfunctioning phones will be returned to study staff if necessary. IT support will be available to troubleshoot phones during regular business hours throughout the study. Study staff will record all instances of malfunctioning phones as part of process evaluations.

**EMAI Application.** The EMAI application for this study will be programmed following user centered design principles on the *emocha* platform.

*Prompts.* The EMAI application will send prompts (audible alert and text message asking them to complete a specific form, no specific health information revealed in prompts) to participants at 3 times: daily, random, weekly. Daily prompts will occur once a day at a scheduled time, a random prompt occurs once a day at an unscheduled time, and a weekly prompt occurs once a week at a scheduled time. The diversity of prompts allows for a range of response patterns. Participants will be allowed to respond to read form and respond to prompts only after entering a password.

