**Table 1: EMA application sample questions.**

Forms	Behavior Domains	Questions
Daily	Smoking, Diet/Alcohol Use, Sexual Activity	Did you smoke today/this week? (yes/no) If so, how many items did you smoke today? (#); Did you eat any vegetables today/this week? (yes/no); Did you use any alcohol today/this week? (yes/no); Did you have any sex with anyone who was not your marital or long-term partner today/this week? (yes/no) If so, did you use condoms? (yes/no)
Random		
Weekly		
Event-contingent	Smoking, Diet/Alcohol Use, Sexual Activity	Checklist Format: Within the past hour, I smoked, ate vegetables, drank alcohol and/or had sex with someone who was not my marital or long-term partner.

In response to data entered by participants, the EMAI application will be programmed with algorithms to provide real-time feedback, i.e. EMI, through tailored health text messages. Only patients randomized to the EMI arm will receive these messages. We will use general health as well as behavior-specific messaging. Examples are shown in Table 2.

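### Does calling the between-arm difference an EMAI effect misstate what the trial estimates, when both arms receive assessment?

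*Combined protocol and SAP*

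**What the plan says.** The Abstract describes two arms from Day 31, assessment questions only or assessment questions plus messages, and then says: "The randomized design will allow for calculation of an estimate of EMAI effect on diet/alcohol, smoking, and sexual behaviors". The same sentence goes on to give the estimate a purpose beyond this pilot: "which will be used to design future, large-scale randomized controlled trials of EMAI". The study hypothesis, also in the Abstract, is narrower: "participants receiving intervention messaging will have improved self-reported health behaviors compared to controls".

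Section 4 (Study Procedures) sets out the exposure. During Days 1-30, "all participants will receive assessment questions only for a 30 day period in order to establish baseline behaviors". After the Day 30 questionnaire, participants are randomised 1:1 to "either continue receiving assessment questions only (control arm) or to also begin receiving intervention messages (intervention arm"). Below Table 1, the messages are identified as the EMI component: the application is programmed "to provide real-time feedback, i.e. EMI, through tailored health text messages", and these go only to the arm randomised to them.

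Section 3 (Background) treats the two components separately. On assessment: "Ecological Momentary Assessment (EMA) appears to reduce recall bias". On intervention: "Ecological Momentary Intervention (EMI) has benefits beyond traditional interventions by allowing for more temporally and spatially appropriate interventions".

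Section 7 (Study Statistics) uses the combined term twice more. The power example refers to a reduction in alcohol use after EMAI, and the paragraph on change in health behaviours opens by hypothesising that EMAI improves them. The same section introduces Table 3 in terms of intervention impact and specifies that change from baseline is compared between the intervention and control arms with mixed effects models.

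**The concern.** EMAI, as the protocol defines it, is assessment and intervention together. The control arm receives the assessment half throughout, and the baseline is also collected under assessment. If repeated self-report changes behaviour, that change is present in both arms and in the baseline, and the between-arm contrast cannot recover it. What is identified is the effect of adding EMI messages to ongoing EMA.

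Read literally, an EMAI effect is a different and possibly larger quantity. The Abstract says the estimate will be used to design later trials. A designer who took it as the effect of the whole package against no package would carry forward the wrong number, and a null result could be misread as showing that the package does nothing. Because the protocol has separate terms for assessment and intervention, the combined term in the estimation text stands out.

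**Working it through.** **1. What each arm receives, by schedule**

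| Period | Control arm | Intervention arm |
|---|---|---|
| Days 1-30 | Assessment | Assessment |
| Days 31-90 | Assessment | Assessment + messages |

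Assessment is scheduled on 90 of 90 days in both arms. Messages are possible on 90 − 30 = 60 days in one arm and 0 in the other. No arm or period is free of assessment, so the randomised contrast is assessment plus messages against assessment only.

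**2. Which contrast Table 3 is attached to**

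Inputs: 120 participants at 1:1, so n = 60 per arm (section 4, Eligibility and Follow-up); control proportion p1 = 0.50 (section 7); reductions r of 20, 30, 40 and 50% (Table 3). Alpha, sidedness and dropout are not stated; I assume two-sided 0.05 and no dropout.

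With p2 = 0.50(1 − r), p̄ = (p1 + p2)/2, s0 = √[2p̄(1 − p̄)/n], s1 = √[(p1(1 − p1) + p2(1 − p2))/n] and d = p1 − p2:

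Power = Φ[(d − 1.96·s0)/s1] + Φ[(−d − 1.96·s0)/s1]

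For r = 50%: p2 = 0.25, p̄ = 0.375, s0 = 0.0884, s1 = 0.0854, d = 0.25. The first term is Φ(0.899) = 0.8157 and the second is negligible.

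| Reduction | p2 | Computed | Stated |
|---|---|---|---|
| 20% | 0.40 | 0.1950 | 0.195 |
| 30% | 0.35 | 0.3816 | 0.381 |
| 40% | 0.30 | 0.6111 | 0.611 |
| 50% | 0.25 | 0.8157 | 0.815 |

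Truncated to three decimals, all four agree. One arm of 60 against a fixed 50% rate gives 0.338, 0.649, 0.893 and 0.986, and none agree. Table 3 is therefore a between-arm calculation, whatever noun the sentence beside it uses.

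**3. The loose wording beside the text that governs it**

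- Abstract, estimate of EMAI effect: the sentence just before it defines the two arms, an earlier paragraph speaks of estimating intervention impact, and the hypothesis names messaging against controls.
- Section 7, power example: *following* can be read as timing, and the same paragraph describes Table 3 by intervention impact.
- Section 7, change in health behaviours: the opening hypothesis is followed in the same paragraph by the actual test, a comparison of intervention and control arms.

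Each loose phrase has a correct statement of the contrast close by.

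**4. What rewording would change**

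The sample size, Table 3, the mixed effects comparison and the hypothesis would all stay as they are.

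**The case for a change.** The strongest case for a change is that a pilot's main product is its estimate. Section 7 says the study exists to give preliminary estimates and is not powered for efficacy, so the identity of the estimate matters more than its p-value. If assessment alone lowers the behaviour, the two effects differ. As a pure assumption, let the whole package take 50% to 25% and assessment alone lower the control rate by 0, 10, 20 or 30%. The control rate is then 0.50, 0.45, 0.40 or 0.35, and the between-arm reduction is 1 − 0.25/0.50 = 50.0%, 1 − 0.25/0.45 = 44.4%, 1 − 0.25/0.40 = 37.5% or 1 − 0.25/0.35 = 28.6%.

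What stands is the distinction itself, and that two sentences (the last of the Abstract's main-objective paragraph and the first on change in health behaviours in section 7) use EMAI as shorthand. The rest does not carry. The range rests on assumed reactivity for which the documents give no figure. No section says later trials will compare EMAI with nothing; the Abstract names no control for them, and the estimate transfers directly to a trial with an assessment-only control. The Abstract also describes EMAI as sampling done in order to deliver interventions. On that reading the arm with messages is the EMAI arm, and its effect is naturally its difference from the stated control. The warning about null results adds little, since the plan already disclaims power for efficacy.

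**Conclusion.** The concern is right about what is randomised but does not call for a change. The label is shorthand that the arm definitions, the hypothesis and the analysis paragraph resolve. An analyst following the plan as written would compare assessment plus messages with assessment only, and would reach a sound conclusion on the hypothesis as stated. The effect on the plan's figures is nil: Table 3 stands, reproduced under an assumed two-sided 0.05 and no dropout. The difference between the effect of added messages and the effect of the whole package cannot be quantified from the documents. This conclusion rests on the plan making no claim about EMAI against no EMAI, and I find none in the protocol.

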## 2. Objectives

**Primary Objective:** To conduct a pilot EMAI study in Rakai, Uganda.

**Secondary Objective:** To assess processes, facilitators, and barriers to EMAI.

**Secondary Objective:** To compare EMAI-collected with traditional questionnaire-collected data.

## 3. Background

**Smartphone-based mHealth is a potentially transformative technology in low and middle-income countries (LMIC).** The growth of mobile phones in LMIC has been remarkable. Initial mobile growth primarily began with “dumb” or feature phones, i.e. mobile devices with limited features and internet connectivity. These devices were rapidly leveraged for health care purposes as part of a “first wave” of applications based primarily on SMS (short message service) technology. Mobile infrastructure has progressively expanded in LMICs and more recently, smartphones have been steadily increasing in number with an estimated 19.8% penetration in 2013, up from 1.6% in 2008. With the increasing adoption of smartphones in LMICs, a “second wave” of mHealth innovation based upon networked, data-driven applications is possible.

**EMAI may outperform traditional methods of data collection and behavioral intervention.** Ecological Momentary Assessment and Intervention (EMAI) is an emerging technique for gathering richer and more relevant data through repeated, longitudinal sampling of participants and intervening in real-time in their *natural setting*. Compared to traditional assessment of human behavior, e.g. questionnaires and interviews, Ecological Momentary Assessment (EMA) appears to reduce recall bias, improve validity by collecting data in the real world, and enable capture of dynamic processes over time, which has also been supported by our own studies which have collected reliable data on geo-located, sensitive behaviors such as drug use, mood, alcohol intake, and sexual behaviors. Ecological Momentary Intervention (EMI) has benefits beyond traditional interventions by allowing for more temporally and spatially appropriate interventions, extending care beyond traditional health facilities and into the individual’s natural setting. Smartphones have revolutionized access to EMAI and provide a growing platform for health-related assessment and intervention in LMICs.

**A disease and prevention/treatment agnostic EMAI platform could be highly scalable.** This study proposes to test a disease and prevention/treatment agnostic EMAI platform. We will test this platform by targeting three behavioral areas of high public health significance, i.e. smoking, diet/alcohol, and sexual activity, which contribute to smoking-related cancers, obesity, and HIV transmission. This agnostic platform could be adapted for most health care conditions, making it highly scalable and increasing potential impact.

**Preliminary studies.** Our group has done extensive and pioneering work in mHealth (including EMAI), mixed methods research, and longitudinal surveillance of health behaviors. *emocha*-We have experience in the design, development, implementation, and evaluation of mHealth as founders of *emocha*, an mHealth software platform. We have conducted a number of EMAI studies domestically, including The EXposure Assessment in Current Time (EXACT) study (5U01DA023832; PI: [name]) assessed drug use and psychosocial stress in injection drug users (IDUs) in urban Baltimore. We developed a EMA application for this study which was successfully implemented with excellent participant response and demonstrated validity. Another EMAI application developed by

Date: March 30, 2015  
Principal Investigator: [name], MPH  
Application Number: IRB00065934

our group to assess HIV care engagement (clinic attendance and adherence), drug cravings, and psychosocial stress to improve retention in care and adherence to medications for out-of-care, HIV-infected IDUs has also been successfully implemented (R34DA033181; PIs: [name], [name]). Finally, we have developed an EMA application to assess alcohol use and sexual behaviors in men who have sex with men in Baltimore which successfully recruited participants (P30AI094189; PI: [name]).

#### 4. Study Procedures

##### **Primary Objective: To conduct a pilot EMAI study with smartphones in Rakai, Uganda.**

**Study design.** This pilot study will be nested within the Rakai Community Cohort Study (RCCS, WIRB #20031318), an ongoing, population-based, prospective, observational study which surveys Rakai District communities in Uganda every ~12-18 months.

**Study setting and population.** Rakai District (~2200 km^2) is a mostly rural district (population~400,000) in Uganda bordered by Tanzania and Lake Victoria. RHSP has been conducting community-based research in Rakai since 1988 including large, prospective health behavior studies. RHSP survey results of demographic and behavioral characteristics are similar to those reported for southwestern Uganda in Demographic and Health Surveys, suggesting that despite long-term surveillance and health education, the population is typical of rural/semi-rural Uganda.

**Rakai Community Cohort Study (RCCS):** RHSP's ongoing 54 community (n~20,000) longitudinal HIV surveillance study provides >20 years of data on HIV prevalence/incidence, health behaviors, sexual networks, and mobility/migration in Rakai District, Uganda.

**Eligibility.** We will aim to recruit 120 total adults (age  $\geq 18$  years) from current, literate RCCS study participants. We will purposely recruit a sample that has a broad range of participant characteristics in our study to optimize diversity of responses and increase study generalizability. Specific variables for which we will target sampling include: gender (~50% female), age (at least 20% among age groups 18-25, 26-35, >50), and occupation (at least 20% traders and farmers).

**Recruitment.** As part of a detailed written informed procedure, RCCS participants have consented to be contacted for future studies. We will enumerate a list of current RCCS participants with key demographics, and, as described above, we will purposely select participants meeting our study population composition goals. We will begin with recruitment via RCCS in locations where it is actively conducting its continual surveys of the Rakai community, asking participants as they undergo the RCCS survey if they would also like to participate in this nested study. If we are unable to conveniently obtain our desired sample via ongoing survey activities of RCCS, we will send trained staff to recruit RCCS participants from communities in which RCCS has recently conducted surveys. Eligible participants will be asked to complete a written informed consent procedure (see Section 8 below) in order to enter this specific study.

**Participant-related Procedures.** *Participant training.* After recruitment, participants will undergo a ~30-60 minute training session. A brief training curriculum will be used consisting of basic phone use,

Date: March 30, 2015

Principal Investigator: [name], MPH

Application Number: IRB00065934

contacting the study team, and detailed instruction on EMAI application use. Participants will be required to demonstrate proficiency with the EMAI interface prior to receiving a study smartphone. The first 48 hours after the participant has the phone will be a “run-in” period to allow for troubleshooting of device problems and to allow participants to become familiar with the EMAI application procedures.

*Follow-up (Days 1-30, Baseline Behaviors).* After the run-in period, all participants will receive assessment questions only for a 30 day period in order to establish baseline behaviors. After completing this initial 30 day period, participants will be required to return to the study office to complete a short questionnaire (see Aim 3) and to be randomized to the second phase of follow-up.

*Follow-up (Days 31-90, Randomized Evaluation).* After completing the Day 30 questionnaire, participants will be randomized using a computerized random number generator, in a 1:1 ratio, to either continue receiving assessment questions only (control arm) or to also begin receiving intervention messages (intervention arm). After reaching 60 and 90 days of follow-up, participants will return to the study office to complete a brief questionnaire on behaviors and experiences with the phone. After 90 days of follow-up participants will also return their phones to study staff.

*Logistics.* Phones will be preloaded with airtime. If additional airtime is needed, participants can “beep” (call and hang up, no cost to caller) study staff to transfer airtime to phones using locally available services.

*Smartphone loss/theft.* Installed software will allow for GPS-locating of lost/stolen phones and can remotely wipe data on phones as needed. Participants will be notified that they will not be eligible for their incentives if they lose or have their phones stolen. These participants will remain in all study analyses (intention-to-treat) but will not receive a second phone.

*Smartphone malfunction.* Participants will be asked to communicate with study staff either in-person or remotely should their smartphone malfunction. Malfunctioning phones will be returned to study staff if necessary. IT support will be available to troubleshoot phones during regular business hours throughout the study. Study staff will record all instances of malfunctioning phones as part of process evaluations.

**EMAI Application.** The EMAI application for this study will be programmed following user centered design principles on the *emocha* platform.

*Prompts.* The EMAI application will send prompts (audible alert and text message asking them to complete a specific form, no specific health information revealed in prompts) to participants at 3 times: daily, random, weekly. Daily prompts will occur once a day at a scheduled time, a random prompt occurs once a day at an unscheduled time, and a weekly prompt occurs once a week at a scheduled time. The diversity of prompts allows for a range of response patterns. Participants will be allowed to respond to read form and respond to prompts only after entering a password.

*Event-contingent reporting.* In addition to prompts, participants will also be able to report behaviors on an event-contingent basis, i.e. within an hour after they engage in a specific behavior. A password will again be required to input data.

*Data collection forms.* The EMAI application will automatically launch the appropriate password-protected forms with each prompt, or they can be launched by the participant for event-contingent reporting. Forms will be completed using touchscreen input. Simple yes/no and multiple-choice check list questions will be used. Forms are designed to be typically completed in <1 minute. Specific form content is shown in Table 1.

*Geolocation.* The EMAI application will automatically record participant geolocation via GPS approximately hourly and each time a form is completed.

*Data transfer.* All participant-entered and geolocated data will be initially stored in encrypted format on the phones. When cellular network or WiFi coverage is detected by the application, the data will be synced to a server for study staff to monitor responses. Updates to forms and algorithms will be sent from the server to phones as needed.

